## 9.0 Study Timelines

- 9.1 The duration of an individual subject's participation is typically less than 45 days, with flexibility to accommodate scheduling.
- 9.2 The end date of the 11-month project period is July 31, 2025. The strict timeline for the entire project and period of award is dictated by this supplement funding mechanism as indicated by the National Institutes of General Medical Sciences Funding Opportunity Announcement and our Notice of Grant Award which is provided with this application.
- 9.3 Given this limited timeline, the funder has required that the IRB approval be reported to the sponsor no later than November 3, 2024. The Notice of Grant Award attached with this application indicates that failure to receive IRB approval by this date could result in suspension and/or termination of the funding for this supplement award.
- 9.4 Primary analyses are expected to be completed within one year of enrollment of the final participant and within two years after the date of approval for research activities to commence.

## 10.0 Inclusion and Exclusion Criteria

- 10.1 Screening procedures, described in the relevant section on recruitment methods, include medical record reviews for alcohol intake and body mass index, as well as age and medical conditions or other conditions which are exclusionary as described below. Prescreening questions and the associated script are provided in an attachment.
- 10.2 Inclusion Criteria. To be eligible, the interested volunteer MUST meet all the following:
  - Be at least 21 years of age.
  - Exceed alcohol intake diagnostic guidelines for MetALD.
  - Have a Body Mass Index (BMI)  $\geq 25$  kg/m^2.
  - Be able to speak and read English or Spanish to provide written informed consent and understand written and oral instructions in English or Spanish.
- 10.3 Exclusion Criteria. To be eligible, the interested volunteer MUST NOT have any of the following:
  - Pre-existing liver disease or hepatocellular carcinoma or prior liver transplant.
  - Pre-existing medical conditions that, in the opinion of the investigative team, would interfere with research participation

(e.g., loss of kidney function, uncontrolled infections, multiorgan failure, uncontrolled upper gastrointestinal bleeding, other active malignancies except skin cancer).

- Pre-existing mental health conditions that, in the opinion of the investigative team, would interfere with the ability to provide informed consent and understand written and oral instructions (e.g., hepatic encephalopathy, psychotic disorder diagnosis or symptoms).
- Current pregnancy.
- Be anyone who, based on self-reported withdrawal symptoms and the opinion of the investigative team, could not currently safely be withdrawn from alcohol without medical detoxification.
- Currently receiving formalized psychosocial treatment for an alcohol use or drug problem and/or newly taking medications for an alcohol use or drug problem.
- Currently receiving formalized behavioral weight management treatment and/or currently taking weight loss medications.

10.4 The research study will exclude anyone who is not an adult, pregnant persons, anyone who is determined to be or suspected to be unable to consent for research participation and will not recruit from prison settings.

## **11.0 Vulnerable Populations**

11.1 N/A. The research is not anticipated to involve individuals who are vulnerable to coercion or undue influence or special populations.

## **12.0 Local Number of Subjects**

12.1 This pilot aims to randomize 40 participants to standard (n=20) and enhanced (n=20) conditions, with randomization stratified by relevant study variables.

12.2 It is anticipated that ~80 interested volunteers may complete informed consent prior to in-person screening to confirm eligibility, allowing for ineligibility and disinterest after screening.

## **13.0 Recruitment Methods**

13.1 The primary recruitment location is our nonprofit partnering clinic, Clínica Esperanza/Hope Clinic (CEHC) at [name]. The CEHC mission, patient population, and resources are described below. Potential participants may also be recruited from the community or via digital outreach with prescreening completed by phone or online with Brown-approved survey software. Procedures may also be implemented at our main laboratory at [name].

13.2 Patient navigators, i.e., Navegantes, are trained community health workers assisting with patient care and outreach for CEHC. The assistance of Navegantes with participant recruitment and retention is key to the success of this research. Study information will be posted and placed in exam rooms, waiting rooms, check-in/checkout windows, and any other locations

within the clinic or in the surrounding community which prospective participants congregate.

- 13.3 Review of the electronic health record (EHR) identifies patients age 21+ years with current drinking levels and body mass index (BMI) placing them at risk for downstream health complications including MetALD. EHR reviews involving access to personally identifying information is necessary to complete the research. A waiver of HIPAA consent is requested via Appendix G attached with this protocol. Where medical history is available in the record, obvious exclusions are identified (e.g., current pregnancy, Hepatitis B/C diagnosis, prior liver transplantation; see Inclusion/Exclusion criteria for a full list of exclusionary criteria). Where feasible, brief alcohol screening via the 3-item Alcohol Use Disorder Identification Test-Consumption subscale (AUDIT-C) is included as part of patient care. The AUDIT-C items, description, and references are provided in an attachment. Generally, the higher the AUDIT-C score, the more likely it is that the patient's drinking is affecting their health or safety.
- 13.4 Patients who may be suitable for the study and who have visits scheduled in advance may be sent a letter informing them that Brown University is recruiting patients in the clinic for a research study. In clinic, patients are invited by their health provider, patient navigator, or Brown University research team member to answer a limited set of prescreening questions to see if the study may be suitable for them. Prescreening questions are in plain language, with many asked in an easy to answer yes/no format. For example, "Are you able to read English or Spanish?" The pre-screening questions and corresponding semi-structured script are provided in an attachment. Potential participants who complete pre-screening may be offered a nominal gift (e.g., a pen, notepad, water bottle) or meal as a gesture of appreciation, consistent with best practices for community engaged research.
- 13.5 If patients are unable to participate in the prescreening at the time of their clinic appointment, prescreening can be completed over the phone or deferred until their next clinic visit. In this case, permission would be requested to remind the patient of their upcoming appointment by common methods (e.g., phone, mail). Potential participants who hear about the study by word of mouth or advertisements in the community or online may also contact the study team by phone, text, or online to hear more about the study and answer the pre-screening questions. In the case of digital outreach with online prescreening, Brown-approved survey software (e.g., Qualtrics or similar) will be used and will include a study landing page that provides enough information to describe study procedures to allow potential participants to decide about their interest in continuing with prescreening. Questions used for online prescreening are the same as those provided in the attachment for phone prescreening and also include the AUDIT-C 3-item alcohol screening measure.
- 13.6 Following pre-screening, participants will continue with informed consent for research participation prior to further screening to confirm eligibility. This last stage of screening includes a blood draw for quantification of liver function and cardiometabolic factors using standard clinical liver, metabolic, and lipid panels, HbA1c, and Hep B/C testing if not already performed (see

Exclusion criteria), as well as a timeline followback interview to assess recent alcohol consumption with high precision.

13.7 To facilitate recruitment and retention, a secure (e.g., Filemaker or similar, Brown-approved software tracking system) tracking database is accessible via an internet connection at CEHC and our Brown University laboratory offices. The tracking database separately stores screening and participant information and can automatically generate study milestones, task reminder emails for staff, and follow-up appointment scheduling and reminders. Given that the target patient population may not have regular access to internet, email scheduling and reminders only supplement efforts of the research team to contact participants by phone or via in-person interactions. Close-contact locators (e.g., spouse, adult children age 18+, close friend) will facilitate future contact. Obtaining contact information for close-contact locators is necessary to complete the research as underresourced participants may not have reliable phone service, internet access, or stable home address. Obtaining locator information is standard practice for research studies working with underresourced and marginalized populations. Research team members stay in touch with participants regularly to promote attendance to the study protocol. The CEHC Navegantes will assist with scheduling participant appointments and following participants through the protocol offering support, reminders, and ample opportunities for interfacing with the study team. Together, these procedures maximize recruitment and retention through minimizing missed appointments and attrition.

13.8 All study advertisements and recruitment materials using the Brown University School of Public Health logo are required to have approval, and appropriate approval will be obtained prior to implementation. Brown university guidelines for teaser and print advertisements will be followed. Print advertisements will include all required information and be similar to the one attached.

13.9 Compensation procedures will be described to participants during the informed consent process. Compensation amounts and the timeline for payments is provided in the bulleted consent form attachment. Interested volunteers are provided \$30 for in-person screening, paid regardless of eligibility. Participants are paid \$150 for the randomization visit and \$150 for the followup visit. Total possible compensation is \$330. Brown university policies and procedures for applying cash payments will be followed with required documentation. Transportation to study visits can be provided at no cost to the participant through Brown-approved and SPH-approved services (e.g., Lyft concierge), public transportation passes, or similar methods. For procedures where participants must arrive fasting (e.g., no food for 3+ hours for Fibroscan®), a meal will be provided. Meals or snacks may also be provided at recruitment events at partnering clinics or other community sites that are easily accessible to the population served.

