## 4.0 Study Endpoints

- 4.1 Primary endpoints include: (a) proportion screened who have alcohol intake and weight-related risks for MetALD; (b) proportion eligible and invited to participate who agree to noninvasive liver imaging with Fibroscan® and arrive for their scheduled appointment; (c) satisfaction with Fibroscan® liver screening; and (d) acceptability metrics for SBIRT/P overall, including retention rates and satisfaction ratings compared across randomized conditions. Satisfaction with Fibroscan liver screening is assessed with a single-item visual analog scale with 0 indicating low satisfaction and 100 indicating high satisfaction. Satisfaction with SBIRT/P overall is assessed with the Client Satisfaction Questionnaire, provided in an attachment.
- 4.2 Secondary endpoints include: (a) self-reported drinking quantity and frequency (e.g., heavy drinking days, drinks per week, alcohol-free days); (b) phosphatidylethanol (PEth), a direct alcohol metabolite biomarker; (c) self-reported weight-related behaviors (e.g., diet quality, eating dysregulation, food cravings, and physical activity); and (d) weight-related biometrics (e.g., body weight, waist circumference, blood pressure). Descriptions and items for secondary-endpoint measures are provided in an attachment. Measures to describe the sample participating in this research, to account for important covariates, and to facilitate team science are also attached. The battery of measures is streamlined from prior projects to reduce staff time, minimize participant burden, and facilitate remote data collection.
- 4.3 Exploratory endpoints include plasma biomarkers to comprise a preliminary panel to screen for likely steatosis and fibrosis in patients at risk for MetALD, with Fibroscan® as a reference standard. These include plasma biomarkers of microbial translocation, innate immune activation, obesity-related metabolic dysfunction, and liver fibrosis.

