## 25.0 Resources Available

- 25.1 There are ample resources available to conduct the research. Data showing the number and demographics of the patient population served by the CEHC provides evidence for the feasibility of recruiting the designated 40 randomized participants within the timeframe expected. The CEHC serves over 4,000 patients over 7,000 visits annually. Patients commonly have indications of cardiometabolic disease, e.g., hypertension (59%), diabetes (41%), and hyperlipidemia (22%). The CEHC has integrated the AUDIT-C screening tool into their clinical procedures, allowing the research team to identify prospective participants based on BMI and alcohol use. Therefore, this study should meet or exceed the goal of recruiting 1 or 2 participants per week to obtain a final sample of 40 randomized participants in the limited project period. Moreover, the research team is fully prepared to expand recruitment through community or digital outreach and conduct study procedures at our Brown SPH laboratory should it be necessary to meet enrollment targets.
- 25.2 The research team includes experienced members in multiple roles (e.g., research assistants, project coordinator, medical laboratory technician, faculty investigators, licensed practitioners, interventionists) contributing effort to the project at our partnering sites, in team meetings, in our laboratory, and in related preparations and efforts. The combined effort devoted to this project for the research team triples the project period or more, indicating a very high level of effort committed by the team.

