STATISTICAL ANALYSIS PLAN

PROJECT TITLE:

Team Science to Identify and Intervene on Metabolism- and Alcohol-Associated Liver Disease (MetALD)

PRINCIPAL INVESTIGATOR:

[name] [name]
Center for Alcohol & Addiction Studies
Center for Addiction & Disease Risk Exacerbation
[contact]
[contact]

DATE OF PLAN:

July 27, 2024

To establish feasibility and acceptability of community-based screening for MetALD, a CONSORT flow diagram reflecting participants' progress through our screening and enrollment process will be created, including the number and percentage of individuals screened for self-reported weight and alcohol-use co-factors who were eligible for noninvasive liver screening (primary outcome measure) and the proportion of those eligible who agreed to non-invasive liver screening (primary outcome measure). These findings will inform how many individuals encountered through our proposed community recruitment efforts exhibit key biobehavioral co-factors for MetALD, the feasibility of reaching them in future studies and the feasibility of conducting noninvasive liver screening with them. To examine the acceptability of noninvasive liver screening, we will assess participant satisfaction with FibroScan® on a 100-point visual analogue scale following baseline procedures (primary outcome measure).

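### Primary endpoint (a) pools people preselected from the health record on drinking and BMI with people who were not, so on its likeliest denominator it cannot show how many people encountered carry the co-factors

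*Protocol*

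**What the plan says.** **The endpoint.** Protocol 4.1 lists as primary endpoint (a) the "proportion screened who have alcohol intake and weight-related risks for MetALD". It does not say at which step a person counts as screened. The SAP's feasibility paragraph gives the matching primary outcome as the number and percentage of "individuals screened for self-reported weight and alcohol-use co-factors who were eligible for noninvasive liver screening". It says these findings will inform "how many individuals encountered through our proposed community recruitment efforts exhibit key biobehavioral co-factors for MetALD" and whether such people can be reached in future studies.

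**The record-based route.** At the primary clinic, record review "identifies patients age 21+ years with current drinking levels and body mass index (BMI) placing them at risk" (13.3). It also removes obvious exclusions where the history is available. Section 25.1 says that AUDIT-C has been built into clinic procedures, "allowing the research team to identify prospective participants based on BMI and alcohol use". Section 13.4 adds: "Patients who may be suitable for the study and who have visits scheduled in advance may be sent a letter".

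**The other routes.** "Potential participants may also be recruited from the community or via digital outreach" (13.1). Section 13.5 lets people who hear of the study by word of mouth or advertising contact the team and be prescreened. The sentence in 13.4 on invitations made in clinic does not restrict them to patients whose record was flagged.

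**A competing definition.** Section 10.1 says that screening procedures "include medical record reviews for alcohol intake and body mass index".

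**The concern.** Drinking level and BMI are used twice: to find clinic prospects, and then as the result that endpoint (a) reports. Among flagged patients, the proportion confirmed at prescreening is in effect the positive predictive value of the flag. Among people who were not preselected, it is the rate of the co-factors in whoever came forward. The plan pools the two, and neither document asks for the result by route or for counts of records reviewed and flagged.

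This is a named primary outcome of a feasibility pilot, and its stated use is planning. A later study that dropped the record step, or recruited through a different mix of routes, could be misled about how many people it must approach. Nobody could correct the figure afterwards if route and record counts had not been logged.

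**Working it through.** **Is there a figure to reproduce?** No. The documents give no expected value, target or precision for endpoint (a), no number prescreened and no share by route. The only related figures, about 80 consented and 40 randomized (40/80 = 50%; Protocol 12.1 and 12.2), concern a later step.

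**Which denominator does the text favour?** The SAP's mention of self-report fits the prescreening survey better than a chart review. Protocol 6.3 says that survey describes the people reached for screening and tracks reasons for ineligibility. Section 10.1 points the other way, so the prescreened reading is the likelier one but not the only one.

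**How far could the pooled figure move on that reading?** All inputs here are assumptions:
- p, the co-factor rate among people encountered: 5% to 30%.
- Se and Sp, the sensitivity and specificity of the record flag: 0.6/0.7 to 0.8/0.9.
- s, the share of prescreened people who were record-flagged.
- Entrants by other routes are given the rate p.

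Formulas:
- Rate among flagged patients: PPV = p·Se / [p·Se + (1 − p)(1 − Sp)].
- Pooled rate: s·PPV + (1 − s)·p.

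With p = 20%:

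| Se/Sp | PPV, which is the pooled rate at s = 1 | Pooled rate at s = 0.5 |
|---|---|---|
| 0.6/0.7 | 0.12/(0.12 + 0.24) = 33% | 27% |
| 0.7/0.8 | 0.14/(0.14 + 0.16) = 47% | 33% |
| 0.8/0.9 | 0.16/(0.16 + 0.08) = 67% | 43% |

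Over the whole assumed range, the pooled rate is 1.5 to 5.9 times p at s = 1, and 1.3 to 3.5 times p at s = 0.5. The extremes at s = 1 are:
- p = 30%, Se/Sp 0.6/0.7: 0.18/(0.18 + 0.21) = 0.462, and 0.462/0.30 = 1.5.
- p = 5%, Se/Sp 0.8/0.9: 0.04/(0.04 + 0.095) = 0.296, and 0.296/0.05 = 5.9.

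At s = 0 there is no inflation from this source.

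**Can the eligibility numerator cancel it?** The SAP counts people who are eligible, which can be fewer than those with both co-factors. The share of carriers who would have to be excluded for other reasons is 1 − p/(pooled rate). With p = 20% and Se/Sp 0.7/0.8 this is 1 − 0.20/0.333 = 40% at s = 0.5, and 1 − 0.20/0.467 = 57% at s = 1. Section 13.3 already removes obvious exclusions from the record route where history is available, which weakens the offset there.

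**Would a records-reviewed denominator solve it?** Not if unflagged patients are counted as negative. The figure is then at most p·Se = 0.20 × 0.7 = 14%, or one in 7.1 instead of one in 5, and lower still if flagged patients decline prescreening. Under 13.3, AUDIT-C is collected only where feasible and history is used only where available, so missed carriers are to be expected.

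**The case against.** A reader might infer that endpoint (a) is measured wholly in people already picked from the record, and is therefore certain to overstate. The documents do not support that, for four reasons:

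- **Not everyone is filtered.** Only the letter in 13.4 is tied to apparent suitability. In-clinic invitations carry no such limit, and community, digital and word-of-mouth entrants bypass the record. This stands. It means the problem is an unrecorded mixture, not uniform preselection.
- **Screening may begin at record review.** Section 10.1 allows that reading, so the inflation is conditional. It does not settle the matter, because the SAP's self-report wording points to the survey and no count of records reviewed is planned.
- **The SAP's claim is tied to its own recruitment efforts.** The percentage can be read as the yield of this pathway, which would serve a later study using the same pathway. That is fair. But such a study would still need the number of records reviewed and the route shares to reproduce the yield. The worry about approaching too few people applies only if the later study changes the pathway.
- **Direction and size are not established.** The eligibility numerator pulls downward, every input above is assumed, and people answering advertisements may differ from clinic patients in either direction. This stands, and only a conditional statement is justified.

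The prescreening survey is an attachment not included in the documents, so it may already record entry route. Neither document says that route would be used in reporting.

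**Conclusion.** The point holds in conditional form. If the denominator is the people prescreened, which is the more natural reading of the SAP, endpoint (a) mixes preselected and unselected people. It then depends on the route mix and is likely to exceed the co-factor rate among all people encountered. It cannot by itself carry the SAP's conclusion about them.

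The size is unknown. The illustrative ratios above rest on assumed prevalence, flag accuracy and route share, and on equal rates in the non-record routes. Other exclusions may offset part of the effect. A firm claim of upward bias, or any single figure for it, would go beyond the documents.

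The randomized comparison is not affected. This is an inexpensive improvement that changes what one primary outcome can support.

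**What to change.** 1. State in Protocol 4.1(a) and the SAP that the denominator is people who complete prescreening.
2. Record entry route for each of them: record-flagged, unselected clinic, or community/digital. Define unselected clinic as invited without reference to the record review. Patients reviewed and not flagged would be depleted of carriers: with p = 20% and Se/Sp 0.7/0.8, their rate is 0.20 × 0.3 / (0.20 × 0.3 + 0.80 × 0.8) = 0.06/0.70 = 8.6%.
3. Report endpoint (a) by route, with the proportion carrying both co-factors shown separately from the proportion fully eligible.
4. Start the planned CONSORT diagram with records reviewed, records flagged (with the number lacking alcohol or BMI data), people approached and people prescreened.
5. Limit the conclusion about people encountered to entrants not preselected from the record, and describe the record-route figure as yield among flagged patients.
6. Do not count unflagged patients as confirmed negatives. Flagged-and-confirmed over records reviewed may be given as a pathway yield, labelled as a lower bound on prevalence.

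The cost is one data field, a de-identified tally kept during recruitment, and a few sentences of text. The tracking database in 13.7 already stores screening information. The drawback is that the route-specific proportions rest on smaller numbers and will be less precise than the pooled figure.
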